Study Procedures	
Following successful screening, enrollment interview and signing of informed consent, participants will be provided with an active Nerivio Migra or identically looking sham device and trained to perform treatment and provide feedback via the smartphone application.
 
Baseline information including mean frequency and severity of migraine attacks, occurrence of other headaches, presence of ICHD-3 diagnostic criteria for migraine with and without aura and use of preventive and rescue medications will be recorded.
 
During roll-in stage, migraine status will be recorded and participants will be requested to complete a quality of life questionnaire.
 
Participants who successfully completed the roll-in stage will continue to the stage involving treatment of four qualifying migraine attacks. A qualifying migraine attack shall be preceded by at least 48 hours of freedom from headache. Participants will be instructed to activate the device at the onset of a qualifying migraine attack and manually adjust stimulation intensity to a level within the pre-defined range where it is perceivable but not painful. Patients will be requested to refrain from use of rescue medications prior to and during the first two hours after treatment with the device, and if they can not comply with this, record their use of medications in the smartphone application. Via the application, each participant will be asked to rate his/her migraine pain level using Pain Grades Scale with values 0-3 (no pain, mild, moderate, severe): (1) upon starting the treatment, (2) two hours after starting treatment, (3) 48 hours after start of the first treatment corresponding to current migraine attack. Participants will be also asked to provide feedback using the application regarding the time elapsed from start of migraine attack to start of the treatment. In addition, participants will be reporting their use of rescue medication and presence of nausea, photophobia, phonophobia and allodynia, as well as additional migraine symptoms.
 
In case of failure to provide feedback regarding pain level post-treatment, queries will be generated via EDC system and telephone follow-up will be performed by study investigator staff to solicit such feedback. After providing feedback at two hours post start of treatment and in case of pain recurrence, participants will be allowed to re-treat the attack using Migra device.
 
Adverse events will be reported.
 
Post study questionnaire will include patient global impression of change, blinding and usability assessments.

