Participants will be instructed to activate the device at onset of a qualifying migraine attack and manually adjust stimulation intensity to a level within the pre-defined range where it is well perceived but not painful. A qualifying migraine attack shall be preceded by at least 48 hours of freedom from headache. Patients will be requested to refrain from use of rescue medications prior to and during the first two hours after treatment with the device, and if they can not comply with this, record their use of rescue medications (migraine specific drugs or other medications or therapies that may be used to treat pain, from a pre-specified list) in the mobile application.

Via the smartphone application, each participant will be asked to rate his/her migraine pain level three times using Pain Grades Scale (0 - no pain, 1- mild pain, 2- moderate pain, 3 – severe pain): (1) upon starting the treatment, (2) two hours after start of treatment, (3) 48 hours after start of attack. At the start of each treatment, participants will be also asked to provide time elapsed from start of migraine attack to start of the treatment. Participants will be also asked to provide feedback regarding their use of medication (migraine specific drugs or other medications or therapies that may be used to treat pain, from a pre-specified list), presence of nausea, photophobia and phonophobia, and treatment perception. After providing feedback at two hours

after start of treatment and in case of pain recurrence, participants will be allowed to re-treat the attack using Migra device.

Adverse events will be reported.

Duration of study participation for each patient will be up to three months, determined by one month of the roll-in stage followed treatment of four qualifying attacks over the course of two months (whichever is achieved first).

Post study questionnaire will include patient global impression of change [27], blinding and usability assessments.

Stage Three. This part will include open label extended treatment. Following the completion of the study by all subjects and the return of all study devices, subjects will be offered a 2-month period of using active device, at no cost.

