6.2.2 Procedures to ensure blinding

This is a double-blind study: neither the patient, nor the investigators will be aware of arm allocation of each study participant. Maintaining double blind design is a known challenge in non-invasive neuromodulation devices trials. A number of means are planned to ensure the double blind aspect of this trial.

Selection of identically looking, active sham devices as control means is only a single step aimed at maintaining blindness. Each device will be numbered with 3 digit numbers, first digit site number and two digit subject numbers. Each new patient will be provided with d next consecutive numbered device.

Adherence to randomization procedure by clinical staff is critically important.

Importance of adherence to study design and procedures will be explained to participants in the course of enrollment.

No information regarding expected stimulation perception will be provided, except for the fact that stimulation intensity adjustment control will allow to adjust intensity to "a well perceived but non-painful" level.

In order to achieve blinding, participants will be trained individually. A training clip will be used for training, in order to minimize staff exposure to participants' reaction to and tolerability of treatment intensity.

In the course of the trial, participants will not be asked directly any questions regarding treatment perception.

The clinical staff will be instructed to not engage in any discussions regarding anticipated treatment perception.

End of study questionnaire will include individual blinding assessment to examine whether the blinding was well maintained throughout the study.

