6.3.2 Secondary Endpoints

Secondary Performance Endpoints

1. The proportion (%) of subjects reporting treatment response at 2 hours post treatment without rescue medications in at least 50% of treated attacks. Treatment response is defined as: pain level reduction from moderate or severe at baseline to mild or pain level of none if treatment started with mild pain
2. Proportion (%) of patients reporting, 2 hours post treatment:
 - freedom from pain (pain grade 0) and their most bothersome migraine-associated symptom (MBS) in at least 50% of treated attacks
 - freedom from nausea in at least 50% of treated attacks
 - freedom from photophobia in at least 50% of treated attacks
 - freedom from phonophobia in at least 50% of treated attacks

6.3.3 Exploratory Endpoints:

1. The proportion (%) of patients reporting freedom from pain (pain grade 0) 48 hours post treatment without medications in at least 50% of treated attacks

2. The percent of subjects who are pain-free at 2 hours with no use of rescue medication, and either have no relapse of pain within the subsequent 46 hours, or, if they have a relapse of pain in this time window, it disappears every time, after two hours, using the device, with no use of rescue medications.
3. Patient global impression of change, with emphasis on disability and quality of life.

6.3.4 Safety Endpoints:

- Treatment tolerability
- Adverse events and complications whether related or unrelated to study device.

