7 STATISTICAL CONSIDERATIONS

7.1 *Study Design and Aim*

The study is designed as a prospective, randomized, double-blind, sham controlled multi-center clinical trial. The study aim is to demonstrate safety and effectiveness of Nerivio Migra electro stimulation device for treatment of migraine attacks with and without aura.

7.2 *Study Variables*

7.2.1 *Primary performance variable*

The primary performance endpoint, the proportion (%) of patients reporting freedom from pain (pain grade 0) 2 hours post treatment without rescue medications in at least 50% of treated attacks, will be measured in the form of a binary variable which will be assigned the value of "1" if the subject reports freedom from pain (pain grade 0) 2 hours post treatment without rescue medications in at least 50% of his/her treated attacks, and "0" otherwise.

7.2.2 *Secondary performance variables*

The secondary performance endpoints will all be expressed in the form of binary variables as in the representation of the primary performance variable.

7.2.3 *Exploratory performance variables*

The exploratory performance endpoint, the proportion (%) of patients reporting freedom from pain (pain grade 0) 48 hours post treatment without rescue medications in at least 50% of treated attacks, will be measured in the form of a binary variable which will be assigned the value of "1"

if the subject reports freedom from pain (pain grade 0) 48 hours post treatment without rescue medications in at least 50% of his/her treated attacks, and “0” otherwise.

Patient global impression of change is measured via a questionnaire.

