Patient global impression of change will be summarized by descriptive statistics per treatment group and compared between the groups with a t-test.

Ease of use will be summarized by descriptive statistics.

7.8.6 *Safety Analysis:*

The primary safety variable, the cumulative incidence (and 95% CI) of device related adverse events (AEs) throughout the study, will be presented in tabular format and will include incidence tables by severity.

Adverse event rates will be compared between the study groups with a chi-squared test.

Serious adverse events will be listed and discussed individually.

Treatment tolerability will be compared between the study groups, the number and percent of subjects who fail to complete the study and the number and percent of subjects who fail to complete the study because of Adverse Events will be presented as well.

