2. In how many days per month, in the last 2 months, was your productivity at work or school significantly reduced because of your migraine (do not include days that you indicated in question #1)?
 1. 0
 2. 1-3
 3. 4-8
 4. More than 8
3. In how many days per month, in the last 2 months, did you not do household work because of your migraine (such as housework, home repairs or maintenance, shopping, caring for children, etc.)?
 1. 0
 2. 1-3
 3. 4-8
 4. More than 8
4. In how many days per month, in the last 2 months, was your productivity in household work significantly reduced because of your migraine (such as housework, home repairs or maintenance, shopping, caring for children, etc.)?
 1. 0
 2. 1-3
 3. 4-8
 4. More than 8

5. On how many days per month, in the last 2 months, did you miss family, social or leisure activities because of your migraine?
 1. 0
 2. 1-3
 3. 4-8
 4. More than 8
6. In the past two months, how would you grade the degradation in your quality of life as a result of migraines?
 1. None
 2. Mild effect
 3. Moderate effect
 4. Severe effect
7. How much do you typically spend on migraine medication, per month, during the 3-months study?
 1. Less than \$10
 2. \$11-\$20
 3. \$21-\$50
 4. More than \$50

Part II – Device Usability and Pricing

1. If you could purchase the device now, how much would you be willing to pay for it, per month?
 1. Less than \$10
 2. \$11-\$20
 3. \$21-\$50
 4. More than \$50
2. If you had the device permanently in your possession, what would be your estimate for additional (extra) spending on medication?
 1. Less than \$10
 2. \$11-\$20
 3. \$21-\$50
 4. More than \$50
3. If you had the device permanently in your possession, what would be your estimate for additional (extra) spending on medication?
 1. Less than \$10
 2. \$11-\$20
 3. \$21-\$50
 4. More than \$50

4. How likely are you to recommend using NM1 device for a friend or family member that also suffer from migraines?
 1. Not likely
 2. Likely
 3. Very likely
 4. Extremely likely
5. How likely would you be willing to share the information about your migraine episodes with your physician or any other designated care-taker, via the device and its App?
 1. Not likely
 2. Likely
 3. Very likely
 4. Extremely likely

Did you experience any inconvenience during the treatment?

6. Itching at the location of the device?
 1. None
 2. Mild
 3. Moderate
 4. Severe
7. Skin redness at the location of the device?
 5. None
 6. Mild
 7. Moderate
 8. Severe

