8. Sensation of heat at the location of the device?
 9. None
 10. Mild
 11. Moderate
 12. Severe
9. Overall, how would you rate the study and your experience with the device?
 1. Excellent
 2. Very good
 3. Good
 4. Fair
 5. Poor
10. How user friendly and intuitive was the App?
 1. Extremely friendly/intuitive

2. Very friendly/intuitive
3. Somewhat friendly/intuitive
4. Not so friendly/intuitive
5. Not friendly/intuitive at all

11. To what extent did you like using the device?

- a. Liked it a lot
- b. Liked it
- c. Did not like it so much
- d. Disliked it very much

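### The End of Study Questionnaire printed in Appendix B contains neither the global impression of change item nor the blinding item that the protocol says it will include

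*Combined protocol and SAP*

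**What the plan says.** The synopsis and section 6.1 make the same commitment about the content of the final questionnaire. Section 6.1 words it as "Post study questionnaire will include patient global impression of change [27], blinding and usability assessments"; the synopsis words it as "Post study questionnaire will include patient global impression of change, blinding and usability assessments". Section 6.2.2, on procedures to protect blinding, is more specific about both place and purpose: "End of study questionnaire will include individual blinding assessment to examine whether the blinding was well maintained throughout the study".

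PGIC is also an endpoint. Section 6.3.3 lists it third among the exploratory endpoints: "Patient global impression of change, with emphasis on disability and quality of life". Section 7.2.3 gives its source ("Patient global impression of change is measured via a questionnaire") and section 7.8.5 its analysis: "Patient global impression of change will be summarized by descriptive statistics per treatment group and compared between the groups with a t-test".

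Appendix B prints the End of Study Questionnaire in full wording with response options. Its first block has 7 items. Its second block, headed "Part II – Device Usability and Pricing", has 11 items, the last of which is "To what extent did you like using the device".

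**The concern.** The body of the protocol and the instrument in its own appendix do not match. An endpoint with a planned test has no matching question on the form said to collect it, and a check written into the blinding procedures has no question at all.

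The blinding check matters more. Every efficacy outcome is reported by the participant. Section 6.1 sets the sham at 0.1 to 0.5 Hz and Appendix A sets the active program at 100 to 120 Hz, so the frequencies differ by a factor of at least 100 / 0.5 = 200, in a stimulus that participants are meant to perceive. Section 6.2.2 itself acknowledges that blinding is difficult in trials of this kind of device. If the trial is positive, readers will ask whether participants knew their arm, and the sponsor would want data that bear on the question.

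Timing adds to this. Under section 6.1, Stage Three offers every participant an active device. A guess collected after that is coloured by comparison of the two devices, so a blinding item omitted at the end-of-study visit cannot be cleanly recovered later.

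**Working it through.** No sample size, power or error-rate figure is involved. The check compares promised content with printed content.

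**Promised (synopsis, 6.1, 6.2.2):** three components, namely PGIC, blinding and usability.

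**Printed (Appendix B, End of Study Questionnaire):**

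- First block, 7 items: 5 on days missed or with reduced productivity (items 1 to 5), 1 on the current effect of migraine on quality of life (item 6), 1 on medication spending (item 7).
- Part II, 11 items: 3 on price and medication spending (items 1 to 3, of which 2 and 3 are identical), 1 on recommending the device, 1 on sharing information with a clinician, 3 on local tolerability (itching, redness, heat), 1 on overall experience, 1 on the app, 1 on liking the device.
- Total: 7 + 11 = 18 items. Items asking for global change: 0. Items asking for a guess of allocation: 0. Usability is covered. Components delivered: 1 of 3.

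**Nearest substitutes on the form:**

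- Item 6 of the first block asks for present status, from none to severe. It is not a rating of change.
- Part II item 9 rates the study and the experience of the device, from excellent to poor. It measures satisfaction, not change in condition, and is not a guess of allocation.
- Items 1 to 6 appear in matching form in the Start of Study Questionnaire. Each has four ordered options, so a change in category of between 1 − 4 = −3 and 4 − 1 = +3 could be computed per item. This is a calculated difference in banded status, not the patient's own overall judgement. No section defines PGIC this way or says how six items would be combined.

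**Other possible sources in the document:**

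- The three app screens in section 6.4.2 (start of attack, 2 hours, 48 hours) contain neither item. Sections 6.1 and 6.4.1 mention feedback on treatment perception through the app, but the printed screens show no such field, and perception of the stimulus is not a guess of allocation in any case.
- Section 6.2.2 says that participants will not be asked directly about treatment perception during the trial. That leaves the final questionnaire as the only stated place for the blinding check.
- The end-of-study visit in section 6.6.2 lists completion of a questionnaire without naming a second one.

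**Analysis side:** section 7.8 names no summary or test of blinding data, so that check lacks both an item and a method. PGIC has a named test (a t-test), but the document gives neither the wording of the item nor its response scale.

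**The case against.** The strongest reply is that the appendix may not be the working form. Section 9 keeps case report forms, the Data Management Plan and the SAP outside the protocol, to be changed without amendment. Section 6.4 refers the structure of the eCRFs to the Data Management Plan, and section 6.4.1 says that end-of-study questionnaires may start as paper worksheets. No section calls Appendix B complete or final. The printed form also looks unfinished: it has a duplicated question, and its response options are numbered 5 to 8 and then 9 to 12 (some of this may come from reading the PDF). This objection stands in part. A reader might infer that blinding and PGIC data will be missing for all 124 to 248 subjects; the documents do not establish that, because a separate form could hold the items. But no section says that one does, and section 6.2.2 places the blinding assessment in the end-of-study questionnaire itself. The inconsistency remains until the sponsor cites a form.

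Second, a reader might infer that the exploratory endpoint has no data source at all. That is too strong. Section 6.3.3 stresses disability and quality of life, and the paired items 1 to 6 cover those topics. What is missing is either a PGIC item or a stated derivation.

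Third, a reader might infer that participants will readily tell the arms apart. The documents give frequencies but no data on how the two programs feel, and section 6.1 says that sham pulses are perceivable, of similar amplitude range and adjustable in a similar way. Nor would an end-of-study guess settle the matter, because perceived benefit influences it. It informs the question and no more.

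Finally, the plan already commits to both assessments, so this is not a criticism of the design. That is correct: the point concerns the instrument, not the intention.

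**Conclusion.** The point holds as a contradiction between the stated plan and its own printed instrument. Two of the three components promised for the end-of-study questionnaire are absent from all 18 printed items, and the document places them nowhere else. If Appendix B is used as printed, the blinding check promised in section 6.2.2 cannot be done, and one of the three exploratory endpoints would have to rest on a derived change that the plan does not describe.

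The size is limited. The primary and secondary endpoints, their tests, the significance level and the sample size are untouched. The conclusion rests on two assumptions: that the printed questionnaire is the one handed to participants, and that no separately held form contains the items. The documents neither confirm nor rule out either assumption. The point is still worth settling before participants reach their end-of-study visit, because the blinding guess is hard to recover afterwards and the correction is very small.

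**What to change.** Add two items to the Appendix B End of Study Questionnaire:

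- one global impression of change item with a stated response scale, so that the comparison in section 7.8.5 has a defined variable;
- one treatment-guess item (active / sham / do not know).

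State that both are completed at the end-of-study visit, before Stage Three and before any disclosure of allocation. The existing visit order already allows this. Add to section 7.8 one descriptive table of the guess by arm.

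If another form already holds these items, cite it in sections 6.1 and 6.2.2 instead. If the sponsor means PGIC to be the change in items 1 to 6, state that derivation and how the items are combined. The duplicated spending question in Part II can be corrected in the same revision.

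The cost is two questions at an existing visit, one form revision and one table.

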6.2 Measures to Minimize Bias

A number of measures are built into the study design and procedures in order to minimize various potential sources of bias.

Implementation of the one-month roll-in period in conjunction with baseline assessment (questionnaire) mitigates recall bias and allows more reliable assessment of baseline headaches frequency, duration and severity.

Gender selection bias will be eliminated due to recruiting patients in headache clinics, emergency and neurology departments.

Randomization is employed to avoid bias in participants' allocation to study arms.

Double blind design ensures collection of bias free efficacy data. Specific measures will be taken to ensure blindness (refer to Section 6.2.2).

Detailed statistical analysis plan will be developed prior to study start to mitigate interpretation bias.

6.2.1 Randomization

Randomized allocation of active and sham devices with stratification to use of preventive medications will be performed. Every site will be allocated a stock of identically looking, numbered devices of both kinds.

6.2.2 Procedures to ensure blinding

This is a double-blind study: neither the patient, nor the investigators will be aware of arm allocation of each study participant. Maintaining double blind design is a known challenge in non-invasive neuromodulation devices trials. A number of means are planned to ensure the double blind aspect of this trial.

Selection of identically looking, active sham devices as control means is only a single step aimed at maintaining blindness. Each device will be numbered with 3 digit numbers, first digit site number and two digit subject numbers. Each new patient will be provided with d next consecutive numbered device.

Adherence to randomization procedure by clinical staff is critically important.

Importance of adherence to study design and procedures will be explained to participants in the course of enrollment.

No information regarding expected stimulation perception will be provided, except for the fact that stimulation intensity adjustment control will allow to adjust intensity to "a well perceived but non-painful" level.

In order to achieve blinding, participants will be trained individually. A training clip will be used for training, in order to minimize staff exposure to participants' reaction to and tolerability of treatment intensity.

In the course of the trial, participants will not be asked directly any questions regarding treatment perception.

The clinical staff will be instructed to not engage in any discussions regarding anticipated treatment perception.

End of study questionnaire will include individual blinding assessment to examine whether the blinding was well maintained throughout the study.

